2.5 Analysis of the primary objective

The primary objective of the LGG cohort is to compare the antitumor activity of dabrafenib in combination with trametinib versus the carboplatin and vincristine, as measured by ORR to study treatment by central independent review assessment using RANO criteria, in children and adolescent patients with BRAF V600 mutation positive LGG whose tumor is unresectable and who require treatment.

2.5.1 **Primary endpoint**

ORR is defined as the proportion of patients with best overall response (BOR) of confirmed complete response (CR) or partial response (PR) according to RANO criteria (see Appendix 3 of the study protocol). ORR will be calculated based on the FAS using central independent review of tumor assessment data. Only tumor assessments performed before the start of any further antineoplastic therapy (i.e. any additional secondary antineoplastic therapy or surgery) will be considered in the assessment of BOR. See Appendix 5.5 for primary estimand definition.

Best overall response

The BOR will be assessed based on reported responses across all evaluation time points. Both CR and PR must be confirmed by repeat assessments performed not less than 4 weeks after the criteria for response are first met. The next scheduled assessment may be used for purposes of confirmation of response. In the absence of a confirming scan 4 weeks later, this response will be considered only stable disease (SD).

BOR for each patient is determined from the sequence of overall responses according to the following rules, up to progression:

- CR = at least two determinations of CR at least 4 weeks apart before progression
- PR = at least two determinations of PR or better at least 4 weeks apart before progression (and not qualifying for a CR)
- SD = requires at least one SD assessment (or better) determined at or beyond the second regularly scheduled tumor assessment (nominally week 16 i.e \geq 105 days allowing for the ±1 week visit window) from randomization (and not qualifying for CR or PR).
- PD = progression after start of study treatment (and not qualifying for CR, PR or SD).
- UNK = all other cases (i.e. not qualifying for confirmed CR or PR and without SD at or beyond the second regularly scheduled post-baseline tumor assessment or progression)

If a patient receives any further anti-neoplastic therapy while on study, any subsequent assessments will be excluded from the BOR determination for the primary endpoint. Further anti-neoplastic therapies will be identified via protocol deviations or from the data collected on 'Anti-neoplastic therapies since last date of study drug' as appropriate.

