2.1.1 General definitions

Investigational drug and study treatment

Study treatment will refer to dabrafenib and trametinib or carboplatin and vincristine combination. *Study drug* will refer to each component of study treatment.

Date of first administration of study treatment

The date of first administration of study treatment is derived as the first date when a non-zero dose of any component of study treatment was administered as per the Dosage Administration eCRF. (Example: if first dose of dabrafenib is administered on 05-Jan-2015, and first dose of trametinib is administered on 03-Jan-2015, then the date of first administration of study treatment is on 03-Jan-2015). For the sake of simplicity, the date of first administration of study treatment will also be referred as *start of study treatment*.

Date of last administration of study treatment

The date of last administration of study treatment is derived as the last date when a non-zero dose of any component of study treatment was administered as per Dose Administration Record (DAR) eCRF. (Example: if the last dabrafenib dose is administered on 15-Apr-2014, and the last dose of trametinib is administered on 17-Apr-2014, then the date of last administration of study treatment is on 17-Apr-2014). Note that for Vincristine and Carboplatin last exposure is different from last administration, please see Section 2.4.1 for further details on the derivation of last exposure.

Study day

The study day, describes the day of the event or assessment date, relative to the reference start date.

The study day is defined as:

- The date of the event (visit date, onset date of an event, assessment date etc.) reference start date + 1 if event is on or after the reference start date;
- The date of the event (visit date, onset date of an event, assessment date etc.) reference start date if event precedes the reference start date.

The reference start date for safety assessments (e.g. AE onset, laboratory abnormality occurrence, vital sign measurement, dose interruption, palatability, Karnofsky/Lansky performance status, etc.) is the start of study treatment.

The reference start date for all other, non-safety assessments (i.e., tumor assessment, survival time, disease progression, tumor response, and patient-reported outcomes (PRO)) is the date of randomization.

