2.2 Analysis sets

Full Analysis Set

The FAS comprises all patients to whom study treatment has been assigned by randomization regardless of whether or not treatment was administered. According to the intent to treat principle, patients will be analyzed according to the treatment they have been assigned to during the randomization procedure. This population will be the primary population for efficacy analyses.

Safety Set

The **Safety Set** includes all patients who received at least one dose of any component of the study treatment. Subjects will be analyzed according to the study treatment they actually received where treatment received is defined as the randomized treatment if the patient took at least one dose of that treatment or the first treatment received if the randomized treatment was never received.

Evaluable Set

The **Evaluable Set** (ES) consists of all evaluable patients in the FAS who meet all of the following four criteria:

- centrally confirmed measurable disease, and
- centrally confirmed positive BRAF V600 mutation, and
- an adequate tumor assessment at baseline (An adequate tumor assessment at baseline refers to baseline measurable disease assessed by investigator and confirmed by central independent reviewer per RANO criteria), and
- either 1) a follow-up tumor assessment at week 8 day 1 visit or later (any assessment on or after day 43 allowing for the time-window around the visit) or 2) disease progression at any time or 3) have discontinued for any reason.

The evaluable set will be used for sensitivity analyses as defined in Section 2.5 and Section 2.7.

Crossover Set

The **Crossover Set** (CS) comprises the subset of patients who were randomized to carboplatin with vincristine control arm and elected to crossover to receive dabrafenib in combination with trametinib treatment after centrally confirmed and RANO-defined disease progression. Only subjects who received at least one dose of crossover treatment will be included in the crossover set.

Patient Classification:

Patients may be excluded from the analysis populations defined above based on specific patient classification rules defined in Table 2-6. Reasons leading to exclusion from analysis sets will be listed.

	-
Analysis set	Criteria leading to exclusion
FAS	Not applicable
Safety Set	No dose of study medication
Evaluable Set	Not centrally confirmed measurable disease at baseline,
	Not centrally confirmed BRAF V600 mutant,

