2.7.1 Secondary endpoints

ORR by investigator review

The evaluation of ORR will be repeated by investigator review assessment as per RANO criteria based on the FAS and the Evaluable Set separately.

Duration of response

DOR only applies to patients whose BOR is CR or PR according to RANO criteria. The start date is the date of first documented response of CR or PR (i.e., the start date of response, not the date when response was confirmed), and the end date is defined as the date of the first documented progression per RANO or death due to any cause. If a patient has not progressed or died or has received any further anticancer therapy at the analysis cut-off date, DOR will be censored at the date of the last adequate tumor evaluation date before the cut-off date or before the start of the new anticancer therapy date, whichever is earlier (see Section 2.7.3).

Novartis
SAP Final CSR LGG

DOR will be analyzed as per investigator and central independent reviewer assessments separately. The analyses of DOR will be based on the FAS and will be repeated based on the Evaluable set.

Progression-free survival

PFS is defined as the time from the date of randomization to the date of the first documented progression or death due to any cause. PFS will be calculated using RANO criteria based on investigators and central independent review of tumor assessments separately. The analysis will include all data observed up-to the cut-off date. If a patient has not progressed or died or has received any further anticancer therapy at the analysis cut-off date, PFS will be censored at the date of the last adequate tumor evaluation date before the cut-off date or before the start of the new anticancer therapy date, whichever is earlier. (See Section 2.7.3 for additional details regarding censoring rules and determination of date of last adequate tumor assessment). Discontinuation due to disease progression (collected on the 'End of treatment' and 'End of post treatment follow up' disposition pages without supporting evidence satisfying progression criteria per RANO will not be considered disease progression for PFS derivation. The analysis will be based on FAS and Evaluable Set separately.

Time to response

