5.6 Estimands

5.6.1 Primary estimand for the primary objective

The primary clinical question of interest is: what is the relative effect of the two treatment strategies in increasing the ORR by independent review as per RANO criteria in children and adolescent subjects with BRAFV600 mutant LGG with PD, regardless of study treatment discontinuation and before start of any new anti-neoplastic therapy.

The justification for the primary estimand is that it will capture the treatment effect of the study drug even after treatment is discontinued, but avoid potential confounding effects of any other new anti-neoplastic therapy.

The primary estimand is characterized by the following attributes:

- 1. Population: all subjects randomized with BRAFV600 mutant LGG with PD following surgical excision, or non-surgical candidates with necessity to begin first systemic treatment because of a risk of neurological impairment with progression. Further details on the population are provided in protocol Section 5.
- 2. Primary Variable: BOR by independent review as per RANO criteria.
- 3. Treatment: the randomized treatment (the investigational treatment dabrafenib plus trametinib or the control treatment vincristine plus carboplatin), regardless of treatment discontinuation.

Handling of intercurrent events:

- **Discontinuation of study treatment for any reason:** Per treatment policy strategy, tumor assessment data collected after discontinuation of study treatment for any reason will be used to derive BOR. This includes subjects who were randomized but not treated.
- Start of new anti-neoplastic therapy: Per while on treatment strategy, tumor assessments collected before start of new anti-neoplastic therapy will be used to derive BOR. Tumor assessments collected on/after the start of new therapy will not be considered for evaluation of BOR.

Summary measure: proportion of subjects with BOR of a confirmed CR or PR by independent review as per RANO criteria between the treatment arms as assessed by the Mantel-Haenszel chi-squared test. See sections 2.5.2 for details.

Sensitivity analyses for primary endpoint/estimand will be performed using the evaluable set, with all other aspects of the estimand as defined above. Additionally, analyses with response as assessed by the investigator (instead of by central review) will be done under the same estimand attributes.

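### LGG best overall response dates PD from the start of treatment while the cohort's other efficacy rules run from randomization, so a documented progression before any dose is read literally as unknown

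*SAP*

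**What the plan says.** All places are in the LGG plan for the final analysis unless stated.

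- **Section 2.5.1, PD line:** "PD = progression after start of study treatment (and not qualifying for CR, PR or SD". LGG Amendment 1, Section 2.5.1, has the same line.
- **Section 2.5.1, SD line, directly above:** the 105-day minimum is counted with the "week visit window) from randomization (and not qualifying for CR or PR".
- **Section 2.5.1, residual category:** "UNK = all other cases (i.e. not qualifying for confirmed CR or PR and without SD at or beyond the second regularly scheduled" post-baseline assessment. The gloss then adds that the patient is also without progression.
- **Section 2.1.1:** "The reference start date for all other, non-safety assessments (i.e., tumor assessment, survival time, disease progression, tumor response" and patient-reported outcomes) is the date of randomization. Efficacy baseline is the last assessment on or before that date.
- **Section 2.2:** "The FAS comprises all patients to whom study treatment has been assigned by randomization regardless of whether or not treatment was administered".
- **Section 2.7.1:** "PFS is defined as the time from the date of randomization to the date of the first documented progression or death due to any cause".
- **Section 5.6.1:** tumor data after treatment discontinuation are used to derive BOR, and "This includes subjects who were randomized but not treated".
- **Section 5.6.2:** with no valid post-baseline assessment BOR is unknown, except where progression is reported. Section 2.5.3 gives the same rule without the exception.
- **Section 2.5.3:** unknown BOR is non-response for ORR. A sensitivity analysis then moves unknown patients step by step from non-responders to responders. It gives each scenario a probability taken from the response rate among patients whose response is not unknown.

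**The concern.** The PD line fits a cohort in which everyone is dosed and time starts at the first dose. That is the HGG cohort: the HGG plans carry the same line, their FAS requires a dose, and their reference date is treatment start. In the LGG plan the SD line was re-anchored to randomization and the PD line was not.

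The result is a gap between categories. A progression found after randomization in a patient not yet dosed, or never dosed, fails the PD condition. The patient reaches unknown only as a leftover, although the gloss on unknown describes patients without progression. If a valid progression scan exists, none of the four reasons for unknown BOR in Section 2.5.4 describes the patient. Two programmers could code the case differently.

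At stake are the BOR distribution, the reasons-for-unknown table, the investigator versus central concordance on BOR, and the unknown-response scenarios in 2.5.3. The last matters most, since a patient known to have progressed would be carried as someone who might have responded.

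**Working it through.** No stated figure is in dispute, so there is none to reproduce. The check compares the rules and then counts the consequence.

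**Step 1. Anchors side by side (LGG)**

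| Rule | Section | Anchor or population |
|---|---|---|
| PD in BOR | 2.5.1 | start of study treatment |
| SD in BOR | 2.5.1 | randomization |
| Study day for tumor assessment, progression, response | 2.1.1 | randomization |
| Efficacy baseline | 2.1.1 | on or before randomization |
| FAS | 2.2 | all randomized, dosed or not |
| PFS | 2.7.1 | randomization, no dosing condition |
| Estimand | 5.6.1 | includes randomized but untreated |

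PD is the only efficacy rule in this list that needs a dose.

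**Step 2. Who is affected**

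All of these must hold:
- a valid RANO progression after randomization;
- no study dose before it;
- no new anticancer therapy before it, since later scans leave BOR anyway (2.5.1).

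Because baseline is fixed at randomization, a scan between randomization and first dose is post-baseline and can show such a progression.

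**Step 3. Effect on response rates**

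- ORR: PD and unknown are both non-response, so the change is 0 for any number k of such patients. The confidence interval and odds ratio use the same counts and do not change.
- CBR: unknown BOR is a non-responder (2.7.3), as is PD, so the change is 0.
- If the patient is dosed later, the lead-in in 2.5.1 ends the response sequence at progression without a dosing condition, so later scans do not create a response.

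**Step 4. Effect on the unknown-response scenarios**

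Inputs: 102 patients randomized 2:1 (LGG Amendment 1, Section 3.1), so 102/3 = 34 control and 68 dabrafenib plus trametinib. The documents do not give k; 0 to 4 in one arm is an assumption.

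Upper scenario = (responders + unknown) / arm size. Each progressed patient filed as unknown adds one to the numerator:

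| k (assumed) | Control, k/34 | Dabrafenib plus trametinib, k/68 |
|---|---|---|
| 0 | 0 | 0 |
| 1 | 2.9 points | 1.5 points |
| 2 | 5.9 | 2.9 |
| 3 | 8.8 | 4.4 |
| 4 | 11.8 | 5.9 |

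The same values are the amount by which the PD row of the BOR table is too low and the unknown row too high.

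The scenario probabilities also shift. With r responders and u unknown among n, the rate used is r/(n − u). Filing k progressed patients as unknown makes it r/(n − u − k), which is larger whenever r and k are above zero.

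**The case against.** The strongest reply is that other text in the same plan already settles the case. Section 5.6.2 lets reported progression override unknown with no dosing condition. Section 5.6.1 brings untreated patients into BOR, the gloss on unknown excludes progression, and 2.1.1 dates progression from randomization. On that reading PD is the only coherent class and the PD line is leftover wording. This stands as evidence of intent. It does not remove the conflict, because the PD line is the operative rule in the primary-endpoint section and 2.5.3 omits the exception.

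Four stronger readings are tempting, and the documents do not support them.

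- **That the patient is always a PFS event, so the BOR and PFS tables must disagree.** Under 2.7.3 this needs a baseline assessment, no prior new therapy, and not two or more missed assessments before the event. A patient who starts other therapy first is censored for PFS and has later scans dropped from BOR, so the tables agree.
- **That no listed reason for unknown BOR fits untreated patients.** The reasons for no valid post-baseline assessment, or for new therapy before the first one, fit an untreated patient who leaves or moves on. The gap concerns only those with a valid progression scan before any therapy.
- **That the plan expects affected patients.** Sections 2.3.1 and 2.5.4 foresee untreated patients, but not untreated patients with a documented progression before other therapy.
- **That the table is in fact wrong by a known amount.** The count is not given and may be zero.

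It is also fair to say that the final analysis is descriptive, and that a change in wording makes the final text differ from Amendment 1, which governed the primary analysis.

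**Conclusion.** The point holds as a wrong anchor in one line of the LGG BOR rules. It is minor. A reader might infer that the primary result is biased; it is not, since ORR, its confidence interval, the odds ratio and CBR are the same under either anchor.

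Under the literal rule, a patient with documented progression before any dose and before other therapy is tabulated as unknown and enters the 2.5.3 scenarios as a possible responder. Each such patient costs 2.9 points in the control arm or 1.5 points in the dabrafenib plus trametinib arm at the upper scenario. These sizes rest on the planned 34 and 68 patients. With no such patient the effect is nil.

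**What to change.** 1. In the PD line of LGG 2.5.1, replace the start of study treatment with randomization and leave the rest of the line as it is.
2. In LGG 2.5.3, add the exception for reported progression that 5.6.2 already has.
3. Record the wording change from LGG Amendment 1 in the document history, and state whether any patient's BOR category differs from the primary analysis because of it.
4. Keep the treatment-start anchor in the HGG plans, where it fits.

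The cost is two short text edits, one history entry and one reference date in the LGG BOR program. No data collection or main response analysis is touched.

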2.5.2 Statistical hypothesis, model, and method of analysis

The primary efficacy analysis will be performed on the FAS. Note that all hypothesis testing was performed at the time of primary analysis and therefore the analysis performed at the time of final analysis will only be considered descriptive and no hypothesis testing will be performed.

ORR will be summarized using descriptive statistics (N, %) by treatment arm along with twosided exact binomial 95% CIs [Clopper and Pearson 1934]. The odds ratio (OR) (dabrafenib + trametinib vs carboplatin + vincristine) and it's 95% confidence interval (CI) will be determined by logistic regression.

2.5.3 Handling of missing values/censoring/discontinuations

Patients with unknown or missing BOR will be counted as non-responders in the analysis of ORR. If there is no baseline tumor assessment, all post-baseline overall lesion responses are expected to be 'Unknown'. If no valid post-baseline tumor assessments are available, the BOR must be "Unknown". For the computation of ORR, these patients will be included in the FAS and will be counted as 'non-responders'. If a subject is determined to have non-measurable disease only, then the category of response can be expanded to include non-CR/non-PD.

A sensitivity analysis will be performed to consider all possible scenarios for patients with unknown response, i.e. progressively from the scenario where all patients with unknown response are considered as non-responders to the scenario where all patients with unknown response are considered as responders. The probability of each scenario based on the observed response rate in the patients without unknown response will also be calculated,

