- All post-baseline assessments have overall lesion response UNK
- New anti-neoplastic therapy started before first post-baseline assessment
- SD and/or unconfirmed CR/PR only occurring prior to week 16 visit

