5.6.2 Handling of missing values not related to intercurrent event

Subjects in FAS with unknown or missing BOR will be noted as such in the appropriate tables/listings and counted as non-responders in the analysis of ORR. If there is no baseline tumor assessment, all post-baseline overall lesion responses are expected to be "Unknown". If no valid post-baseline tumor assessments are available, the BOR must be "unknown" unless progression is reported.

For the purpose of primary analysis, subjects with a BOR of "unknown" (UNK) will be treated as non-responders in estimating the ORR in the FAS.

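### The LGG sensitivity analysis for unknown response lets patients whose non-response is already settled count as responders, so its range is too wide and its scenario probabilities are wrong for them

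*SAP*

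**What the plan says.** All places are in the LGG final SAP unless stated.

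- **Primary handling (2.5.3).** "Patients with unknown or missing BOR will be counted as non-responders in the analysis of ORR".
- **Sensitivity analysis (2.5.3).** Scenarios run progressively from every unknown patient being a non-responder up to "the scenario where all patients with unknown response are considered as responders". The section adds: "The probability of each scenario based on the observed response rate in the patients without unknown response will also be calculated". It makes no distinction by reason for unknown.
- **BOR categories (2.5.1).** Unknown is whatever is left after confirmed CR or PR, SD and PD. Death is not a category. The PD rule is "PD = progression after start of study treatment (and not qualifying for CR, PR or SD", whereas the SD rule counts from randomization.
- **No valid scan.** 2.5.3 opens "If no valid post-baseline tumor assessments are available, the BOR must be" unknown and stops there. 5.6.2 gives the same rule but adds "unless progression is reported".
- **Reasons for unknown (2.5.4).** One listed reason is "New anti-neoplastic therapy started before first post-baseline assessment". Another is early SD or unconfirmed CR/PR seen only before week 16.
- **Primary estimand (5.6.1).** "Tumor assessments collected on/after the start of new therapy will not be considered for evaluation of BOR".
- **Population (2.2).** The FAS includes patients who were randomized but never treated.
- **Status (2.5.2).** The final analysis is descriptive, with no hypothesis test.

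**The concern.** A sensitivity analysis for missing response should vary outcomes that could have been a response and were not observed. Here it varies a residual class that also holds patients whose status the plan has already settled. A patient who starts new therapy before the first scan cannot have a qualifying response under 5.6.1. A patient who dies before any valid scan can never have a confirmed one. Counting such patients as responders describes data sets that the estimand does not allow.

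Two things follow. The range of odds ratios is wider than the missing data justify, most so if settled patients are concentrated in one arm. The scenario probabilities also give a positive chance of response to patients whose chance is zero. With a design control arm of 34, a few such patients can decide whether the reported interval includes 1.

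**Working it through.** **1. Who falls into unknown under the written rules**

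- *New therapy before the first scan.* 2.5.4 lists this as a reason for unknown, and 5.6.1 excludes all later scans. Non-response is settled.
- *Death before any valid scan.* Death is not a BOR category, so without reported progression the patient lands in the residual class. No confirmed response is possible. Settled.
- *Reported progression, no valid scan.* This is PD under 2.5.1 and not unknown under 5.6.2. It is unknown only if 2.5.3 is followed literally. The corresponding HGG text (HGG final SAP, missing-values paragraph in 2.5.2) carries the exception, so the LGG omission looks like a drafting slip.
- *Progression in a never-treated patient.* The PD rule needs progression after start of treatment, so this patient does not meet it. The definition of unknown also presumes no progression. The category is undefined.
- *Only early SD or unconfirmed CR/PR.* Listed in 2.5.4 as unknown. Without a later scan the outcome is genuinely unresolved, and the patient belongs in the scenarios.

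**2. Inputs for the size**

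The SAP gives no figure for this analysis and no count of unknowns, so the counts are assumptions shaped on the LGG design (LGG SAP Amendment 1, Section 3.1): 102 patients at 2:1, hence 68 and 34, with response rates of 50% and 20%. As an anchor, the stated 80% power reproduces at 79.8% with a continuity correction and 81.1% with Fisher's test.

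- Dabrafenib plus trametinib (D+T): 50% of 68 = 34 responders, 34 non-responders.
- Control: 20% of 34 = 6.8, taken as 7 responders, 27 non-responders.
- Assumed: 5 of the 27 control non-responders are unknown, 3 of them settled and 2 unresolved. No D+T patient is converted.

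**3. Odds ratios**

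OR = (34/34) / (c/(34 − c)) = (34 − c)/c, where c is the number of control responders. Wald interval: exp(ln OR ± 1.96 × SE), with SE = √(1/34 + 1/34 + 1/c + 1/(34 − c)).

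| Control unknowns counted as responders | c | OR | SE | 95% CI |
|---|---|---|---|---|
| none (primary handling) | 7 | 27/7 = 3.86 | 0.489 | 1.48 to 10.05 |
| the 2 unresolved only | 9 | 25/9 = 2.78 | 0.458 | 1.13 to 6.82 |
| all 5, as 2.5.3 allows | 12 | 22/12 = 1.83 | 0.433 | 0.78 to 4.28 |

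Converting control unknowns one at a time, with a nominal one-sided Mantel-Haenszel p: 3 conversions give 0.0245, 4 give 0.046 and 5 give 0.081. The OR reaches 1.00 at 10 conversions and falls below 1 (0.89) only at 11.

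The literal end scenario converts both arms. With 3 D+T and 5 control unknowns the result is 37/68 versus 12/34, OR 2.19, nominal p 0.035.

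**4. Scenario probabilities**

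- As written, with the control arm's own rate: 7/29 = 24.1%. P(all 5 respond) = 0.241⁵ = 0.0008. P(none respond) = (22/29)⁵ = 0.251.
- P(at least one of the 3 settled patients is counted as a responder) = 1 − (22/29)³ = 0.56. The correct value is 0.
- With the 3 settled patients entered as known non-responders, the rate is 7/32 = 21.9%. P(neither of the 2 unresolved responds) = (25/32)² = 0.610. P(both respond) = (7/32)² = 0.048.
- 2.5.3 does not say whether the rate is pooled or by arm. Pooled it would be 41/97 = 42.3%, and P(all 5 respond) = 0.013, about 16 times the control-arm figure.

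**The case against.** The strongest reply is that 2.5.3 describes a graded range with a probability on each step. An extreme bound is meant to be extreme, and a result that survives the wider range also survives the narrower one. That stands as far as it goes: all 5 unknown controls responding has a probability of only 0.0008 here. It does not rescue the probabilities, which are wrong for settled patients at every step, and it gives no help when the result survives only the narrower range.

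Several stronger readings are tempting and should not be adopted.

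- *The analysis can reverse the finding.* Not supported. No unknown counts are given, no test is planned, and the example still favours D+T at 1.83. On these counts reversal needs 11 of 34 controls (32%) converted with no D+T conversions.
- *Patients with reported progression are classed as unknown.* Only through the conflict between 2.5.3 and 5.6.2; 2.5.1 makes post-treatment progression PD.
- *This is the only robustness analysis of ORR.* 2.5.4 also plans an Evaluable Set analysis, a new-therapy analysis if data permit, and possible scenarios for untreated patients, and it tabulates reasons for unknown. 2.5.3 is the only firmly planned one that varies the unknown outcomes.
- *The arms cannot vary separately.* 2.5.3 refers to all possible scenarios and can be read to include cross-arm combinations. It is under-specified on this, not restrictive.

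It is also true that the PD time origin does not affect the primary ORR, since PD and unknown both count as non-response.

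**Conclusion.** The concern holds in a limited form. Followed as written, 2.5.3 produces scenarios that the primary estimand or an early death rules out, and gives those patients a positive probability of response. This is a wrong rule, not merely missing detail. The 2.5.3 and 5.6.2 texts also disagree on reported progression, and 2.5.1 dates SD and PD from different origins in a population that includes untreated patients.

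On the assumed counts, the upper scenario moves from OR 2.78 (1.13 to 6.82) to 1.83 (0.78 to 4.28), so the interval can come to include 1 while the direction is unchanged. This rests on 5 unknown controls, 3 of them settled, and no conversions in the D+T arm. With fewer settled patients, or with conversions in both arms, the effect is smaller. The primary ORR is untouched and no test decision depends on the analysis. What would be misreported is how robust the comparison is to missing response.

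**What to change.** 1. In 2.5.3, add the exception for reported progression, to match 5.6.2.
2. In 2.5.1, count LGG progression from randomization, as SD already is.
3. In every scenario, keep as non-responders the unknown patients with reported progression, death before a valid scan, or new anti-neoplastic therapy before the first scan.
4. Vary only the remaining unknown patients. Keep in this group those with only early SD or unconfirmed CR/PR and no later scan. Limiting the scenarios to patients without any valid assessment would wrongly drop them, although they are among the most plausible unobserved responders.
5. Run the scenarios by arm and state that the probabilities use arm-specific response rates.

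The cost is SAP wording and light programming for one descriptive sensitivity analysis. No new data are needed, since reasons for unknown are already to be tabulated.
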